9.3. Presentation of Concentration Data

9.3.1. Handling of Missing Data

Missing concentration data for all participants who are administered scheduled study treatments will be considered as non-informative missing and will not be imputed. No concentration estimates will be provided for missing sample values.

For the derivation of AUC and for the individual serum concentration versus time curves, the following rules will apply:

- Concentration values below the assay's lower limit of quantification (BLQ) in pre-dose Day 1 samples will be treated as zero;
- The sampling time of pre-dose samples relative to dosing will also be treated as zero;
- BLQ's between two quantifiable samples will be set to missing;
- The first BLQ after the last measurable sample will be set to missing; any subsequent BLQ's will be set to zero.

For serum concentration summary, the following rules will apply:

- All BLQ values will be set to zero;
- No further imputation will be applied to any missing values.

9.3.2. Listing and Presentation of Individual PK Data

The actual and nominal sampling times of PK blood sample collection will be listed for each participant and will include the deviation in time from the protocol scheduled time (*i.e.*, nominal time), if applicable.

All measured concentrations will be presented in original precisions (*i.e.*, significant figures) and units as reported by Bioanalytical lab – *e.g.* ng/mL.

Serum concentrations and time deviation data will be presented in a data listing by participant.

This document is confidential.

9.3.3. Summary of PK Concentrations by Matrix

Serum concentration data will be summarized separately by time point for each cohort/actual treatment, using the following descriptive statistics: number of participants, arithmetic mean, STD, CV, geometric mean, geometric CV, median, minimum, and maximum.

Mean (STD) serum concentration versus scheduled time profiles will be presented in figures on both linear and semilogarithmic scales. Individual serum concentration versus actual time profiles will be presented similarly.

9.4. PK Parameters Derivation

- The apparent C_{max} and the corresponding t_{max} will be read directly from the concentration-time plot (observed data).
- AUC_t will be calculated using the log-linear trapezoidal interpolation rule for extravascular model.
- The terminal elimination rate constant (λ_z) will be determined by log linear regression obtained on at least the 3 last quantifiable concentrations and will not include C_{max} ; $t_{1/2}$ is calculated by the program as $\ln 2/\lambda_z$;
- The AUC_∞ will be calculated by the program as $AUC_\infty = AUC_t + AUC_{extrap}$ where last is the sampling time point of the last measurable concentration (t_{last}). AUC_{extrap} is calculated by the program as: C_{last}/λ_z , where C_{last} is the observed concentration at time t_{last} and λ_z is the elimination rate constant during the apparent terminal elimination phase; AUC_∞ will only be presented for participants with a reliable λ_z ;
- CL will be calculated by program as $(dose/AUC_\infty)$;
- V_d will be calculated by the program as $(dose/AUC_\infty)/\lambda_z$.

The following PK acceptance criteria will be applied to assess the reliability of elimination parameters:

- Number of points to calculate λ_z is greater than or equal to 3 excluding C_{max} point;
- The adjusted square of the correlation coefficient or coefficient of determination (Rsquare adjusted) for the goodness of fit of the regression line through the data points must be ≥ 0.80 ;
- $AUC_{extrap} \leq 20\%$.

Unreliable PK parameters will be listed but flagged and excluded from summary.

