Injection/infusion site evaluation ^f		X		X	X	X	X	X	X	X
Immunogenicity (ALXN1820 ADA) ^g		X								
Review safety card ^h	X				X					X
Concomitant medications		←Monitor continuously→								
Adverse events ⁱ		←Monitor continuously→								
Prophylactic antibiotic tx ^j		←Antibiotic prophylaxis→								

^a Permissible windows for study assessments are described in the Study Operations Manual.

^b Participant will be discharged from the CRU after completing all Day 9, Day 16 or Day 23 assessments. Participants will be provided a “Study Participant ID card” with information for healthcare provider and participant on symptoms of meningitis infection.

^c Non-fasting blood samples will be obtained.

^d Serum pregnancy test for all female participants of childbearing potential to confirm that a female participant is not pregnant prior to dosing.

^e Continuous cardiac monitoring from 1 hour pre-dose to 2 hours after the start of study drug administration.

^f Injection/infusion site reaction evaluation will continue until the reaction is fully resolved.

^g In case of any suspected case of hypersensitivity or anaphylaxis additional samples for the assessment of ADA may be collected at or near the time of the event.

^h The Investigator or qualified designee will meet with the participant at each visit to ensure they carry the clinical trial participant safety card at all times and to review the potential meningococcal infection risks of ALXN1820, and to address any safety concerns of the participant.

ⁱ Collection of adverse events and serious adverse events will begin after ICF signing.

^j Participants will be administered prophylactic antibiotic treatment, oral penicillin V 500 mg twice daily (equivalent to 1×10^6 units), beginning on the evening of Day -1 through Day 155, or until complement activity has normalized (as determined by CAP assay). If penicillin is not tolerated, second line antibiotics will be initiated at the discretion of the Investigator.

Abbreviations: ADA = antidrug antibody; CAP = complement alternative pathway; CRU = clinical research unit; ECG = electrocardiogram; EOI = end-of-infusion/injection; h = hour; ICF = informed consent form; ID = identity; min = minutes; OP = outpatient; PD = pharmacodynamic(s); PK = pharmacokinetic(s); SOI = start of infusion/injection; tx = treatment.

Table 8: Schedule of Activities – Day 36 Through Day 155 for Multiple Dose Cohorts 8 and 9

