Abbreviations: ADA = antidrug antibody; CAP = complement alternative pathway; CRU = clinical research unit; ECG = electrocardiogram; EOI = end-of-infusion/injection; h = hour; ICF = informed consent form; ID = identity; min = minutes; OP = outpatient; PD = pharmacodynamic(s); PK = pharmacokinetic(s); SOI = start of infusion/injection; tx = treatment.

Table 11: Schedule of Activities – Day 22 Through Day 155 for Multiple Dose Cohorts 10

Study Day ^a	Day 22 (168 h post SOI)	Day 29	Day 36	Day 43	Day 50	Day 57	Day 71	Day 85	Day 99	Day 113	Day 127	Day 141	Day 155 ^b /ET
Window (Day)		±1	±1	±1	±1	±1	±1	±1	±1	±1	±1	±1	±1
Status (OP or CRU)	OP	OP	OP	OP	OP	OP	OP	OP	OP	OP	OP	OP	OP
Physical examination	X												X
Abbreviated physical exam (optional)		X	X	X	X	X	X	X	X	X	X	X	X
Vital sign measurements	X	X	X	X	X	X	X	X	X	X	X	X	X
Triplicate ECG	X					X	X		X		X		X
Chemistry ^b	X					X							X
Hematology	X					X							X
Coagulation	X					X							X
Urinalysis (via dipstick)	X					X							X
Serum pregnancy test		X				X		X		X			X
PK samples	X	X	X	X	X	X	X	X	X	X	X	X	X
PD panel (serum total and free properdin, CAP activity)	X	X	X	X	X	X	X	X	X	X	X	X	X
Exploratory biomarkers ^c	X				X								X
Immunogenicity (ALXN1820 ADA) ^e		X			X		X		X		X		X ^d
Review safety card ^f	X	X	X	X	X	X	X	X	X	X	X	X	X
Concomitant medications	←Monitor continuously→												
Adverse events ^g	←Monitor continuously→												
Prophylactic antibiotic tx ^h	←Antibiotic prophylaxis→												

^a Permissible windows for study assessments are described in the Study Operations Manual.

^b Non-fasting blood samples will be obtained.

^c Collection of blood (for serum, citrated and K2-EDTA, or Plasma P100 plasma) and urine.

^d Participants who are ADA positive at Day 155/ET will be followed up to 1 year from the study drug administration or ADA titers return to baseline levels (whichever occurs first).

^e In case of any suspected case of hypersensitivity or anaphylaxis additional samples for the assessment of ADA may be collected at or near the time of the event.

^f The Investigator or qualified designee will meet with the participant at each visit to ensure they carry the clinical trial participant safety card at all times and to review the potential meningococcal infection risks of ALXN1820, and to address any safety concerns on the part of the participant.

^g Collection of adverse events and serious adverse events will begin after ICF signing.

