4.2. Scientific Rationale for Study Design

As this is the first time ALXN1820 will be dosed in humans, a randomized, double-blind, placebo-controlled, single- and multiple ascending dose design was chosen for initial assessment of the safety, tolerability, PK/PD, and immunogenicity of ALXN1820 SC and ALXN1820 IV.

The ALXN1820 IV cohort will provide the reference arm for assessing ALXN1820 SC absolute bioavailability.

This study is being conducted in healthy participants, not patients, so that the assessments are not confounded by disease activity, comorbidities, or concomitant medications. A sentinel dosing paradigm is being used since this is the first administration of ALXN1820 to healthy participants.

The ALXN1820 multiple-dose SC cohorts will assess safety, tolerability, PK/PD, and immunogenicity after multiple doses of ALXN1820 administration. The ALXN1820 multiple-dose SC cohort in participants of Japanese ethnicity will assess safety, tolerability, PK/PD, and immunogenicity after multiple doses of ALXN1820 administration in participants of Japanese ethnicity and comparison of safety and PK/PD between Japanese and non-Japanese participants.

The expected terminal elimination half-life for the highest SC dose being evaluated in this study is expected to be approximately 24 days. The 126 and 154-day washout periods for the single and multiple dose cohorts, respectively, correspond to more than 5 half-lives, at which point ALXN1820 is expected to be nearly completely eliminated from the systemic circulation and complement activity restored to normal levels in the study participants.

As this is a FIH study, placebo control is implemented in each cohort. Due to the difficulty of providing a matching placebo, participants randomized to placebo will receive an equivalent volume of normal saline (SC administration) or 5% dextrose or glucose (IV administration) at the same injection/infusion rate as the active treatment. To ensure double-blinded conditions, the pharmacist preparing the study drug and the physician(s) administering the active treatment or placebo will be unblinded to treatment assignment. All other study personnel will remain blinded to treatment assignment, unless pre-specified in the protocol. All necessary steps will be taken to avoid inadvertent unblinding.

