9.4.3. Other Analyses

9.4.3.1. Pharmacokinetic Analyses

All PK analyses will be performed on the PK Population and will be reported by cohort and study intervention within each cohort (ie, ALXN1820 or placebo).

The individual serum concentration data from participants who receive ALXN1820 SC or ALXN1820 IV with actual sampling dates and times will be used to derive the PK parameters by noncompartmental analyses methods.

The following PK parameters as appropriate and data permitting will be derived:

Parameters	Dosing Regimen	Definitions
C_{max}	SD, MD	Maximum observed serum concentration
t_{max}	SD, MD	Time to maximum observed serum concentration
[name]	Area under the serum concentration versus time curve from time 0 to the last quantifiable concentration
AUC_{tau}	MD	Area under the concentration-time curve during the dosing interval
$AUC_{0-\infty}$	SD	Area under the concentration-time curve from time 0 (dosing) to time infinity
$t_{1/2}$	SD, MD	Terminal elimination half-life
λ_z	SD, MD	Terminal-phase elimination rate constant
CL or CL/F	SD	Total body clearance or apparent clearance
V_d or V_d/F	SD	Volume of distribution or apparent volume of distribution
F	SD	Absolute bioavailability
R_{ac}	MD	Accumulation ratio

Abbreviations: SD = single-dose; MD = multiple-dose

The absolute bioavailability for the ALXN1820 SC cohorts will be defined by the ratio of the geometric means for the $AUC_{0-\infty}$ (area under the concentration-time curve from time 0 [dosing] to time infinity) parameter for the ALXN1820 SC cohort over the ALXN1820 IV cohort. For the absolute bioavailability estimates, a 95% CI for each of the ratio of the geometric means will be provided.

Additional details will be provided in the SAP.

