9.2. Serum PK Endpoint

The following PK parameters will be derived from the serum concentrations of ALXN1820:

For the single dose cohorts 1-7, PK parameters will be derived on Day 1.

For the multiple dose cohort 8, PK parameters will be derived on Day 1 and 29.

For the multiple dose cohorts 8 and 9, PK parameters will also be derived on Day 8, 15 and 22 (when possible using limited sampling schedule up to 24h*).

For the multiple dose cohort 10, PK parameters will be derived on Day 1, 8 (when possible using limited sampling schedule up to 24h*) and 15.

* Only selected PK parameters might be derived due to limited sampling up to 24 h such as C_{max} , t_{max} , and AUC_{0-24} etc.

Refer to Section 1.3 of the Protocol for the full sample schedule.

Parameters	Dosing	Definition
C_{max}	SD, MD	Maximum observed serum concentration
t_{max}	SD, MD	Time to maximum observed serum concentration
[name]	Area under the serum concentration versus time curve from time 0 to the last quantifiable concentration
AUC_{tau}	MD	Area under the concentration-time curve during the dosing interval
$AUC_{0-\infty}$	SD, MD	Area under the concentration-time curve from time 0 (dosing) to time infinity
$t_{1/2}$	SD, MD	Terminal elimination half-life
λ_z	SD, MD	Terminal-phase elimination rate constant
CL or CL/F	SD, MD	Total body clearance or apparent clearance
V_d or V_d/F	SD, MD	Volume of distribution or apparent volume of distribution
F	SD	Absolute bioavailability
R_{ac}	MD	Accumulation Ratio

Abbreviations: MD = Multiple-dose; SD = Single dose

This document is confidential.

Note: tau is the dosing interval for steady-state data, *i.e.*, the time between doses (tau = 1 week).

The absolute bioavailability for the ALXN1820 SC cohorts will be defined by the ratio of the geometric means for the AUC_{0-∞} parameter for the ALXN1820 SC cohort over the ALXN1820 IV cohort. For the absolute bioavailability estimates, a 95% CI for each of the ratio of the geometric means will be provided.

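### SAP 9.4 gives only single-dose formulas for CL/F and Vd/F; applied to the last-dose profiles of the multiple-dose cohorts, with one weekly dose in the numerator, they come out about 50% to 71% too low

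*SAP*

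**What the plan says.** The parameter table in Protocol 9.4.3.1 marks CL or CL/F ("Total body clearance or apparent clearance"), Vd or Vd/F and AUC∞ for single dose only. The table in SAP 9.2 marks the same three for single and multiple dose. For the five-dose regimen SAP 9.2 states "For the multiple dose cohort 8, PK parameters will be derived on Day 1 and 29"; for the three-dose regimen the sentence begins "For the multiple dose cohort 10, PK parameters will be derived on Day 1, 8" and goes on to Day 15. Days 29 and 15 are the days of the last dose.

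SAP 9.4 has one formula for each parameter: "CL will be calculated by program as" dose/AUC∞, and Vd as (dose/AUC∞)/λz. It does not say which dose or which time zero applies after repeated dosing. It also sets reliability criteria, including an extrapolated share of AUC of no more than 20%, and adds: "Unreliable PK parameters will be listed but flagged and excluded from summary".

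SAP 9.6 and SAP 14 record no change from the protocol.

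**The concern.** Dose/AUC∞ estimates clearance only when the AUC in the denominator comes from the dose in the numerator. After the fifth or third weekly dose of a drug with a half-life of weeks, much of the AUC from that point to infinity belongs to the earlier doses. One weekly dose over that AUC gives a clearance that is too low, and Vd inherits the same factor.

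Multiple-dose PK parameters are a secondary endpoint. Cohort 3 (150 mg once) and Cohort 8 (150 mg weekly, five times) use the same dose, so their CL/F values will be read side by side. A drop that comes only from the formula could be taken for time-dependent clearance.

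**Working it through.** **Inputs from the documents**

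- Dosing interval: 7 days (SAP 9.2).
- Half-life: Protocol 4.2 says "The expected terminal elimination half-life for the highest SC dose being evaluated in this study is expected to be approximately 24 days". No value is given for other doses, so I vary it from 10 to 24 days; everything below 24 is an assumption.
- Sampling after the last dose runs to Day 155 (Protocol 1.3, Table 8, "Day 36 Through Day 155 for Multiple Dose Cohorts 8 and 9", and Table 11, "Day 22 Through Day 155 for Multiple Dose Cohorts 10"). That is 155 − 29 = 126 days for Cohort 8 and 155 − 15 = 140 days for Cohort 10.

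The documents give no figure for this bias. Their related figures do reproduce: 126/24 = 5.25 half-lives (Protocol 4.2 says more than 5), and the AUC safety margins in Protocol Table 16 are 1,230,000/16802 = 73 and 1,230,000/22901 = 54.

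**Size of the bias.** Let k = ln2/t½ and r = exp(−7k). Under linear superposition, AUC∞ from the last of n weekly doses is S times the AUC∞ of one dose, where S = 1 + r + … + r^(n−1). One weekly dose over that AUC returns CL/S, so the understatement is 1 − 1/S. λz is unchanged, so Vd has the same error.

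At 24 days r = 0.817. For n = 5, S = 1 + 0.817 + 0.667 + 0.545 + 0.445 = 3.475; for n = 3, S = 2.484.

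| t½ (days) | S, 5 doses | too low by | S, 3 doses | too low by |
|---|---|---|---|---|
| 10 | 2.371 | 57.8% | 1.995 | 49.9% |
| 15 | 2.900 | 65.5% | 2.247 | 55.5% |
| 20 | 3.262 | 69.3% | 2.400 | 58.3% |
| 24 | 3.475 | 71.2% | 2.484 | 59.7% |

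**Sensitivity**

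- First-order SC absorption with rate ka (absorption half-life assumed 1 to 3 days) replaces each exp(−7ki) by the amount not yet eliminated at 7i days, [ka·exp(−7ki) − k·exp(−7ka·i)]/(ka − k). The ranges become 60.4–73.6% (five doses) and 52.5–62.4% (three doses).
- Protocol Table 16 predicts AUC0–168 rising from 4414 to 16802 by the fifth dose (3.81-fold) and from 8497 to 22901 by the third (2.70-fold). Used in place of S, these give 1 − 4414/16802 = 74% and 1 − 8497/22901 = 63%, with no assumed half-life.
- At a half-life of 7.6 days the understatement is still 51% and 45%.

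**Does the reliability screen catch it?** The extrapolated share is exp(−k·T), with T the observed time.

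- Last dose, 24 days: exp(−126k) = 2.6% (Cohort 8) and exp(−140k) = 1.8% (Cohort 10); near zero at 10 days. Both pass the 20% limit.
- Day 1 profile, 7 days until the next dose: exp(−7k) = 62% at 10 days and 82% at 24 days. These fail and are excluded.

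The multiple-dose values that reach the summaries in SAP 9.4.1 are therefore the biased ones. Relative to single-dose values they would sit at 1/S: 29–42% for five doses and 40–50% for three.

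**Cohort 9 versus Cohort 8.** With equal half-lives S cancels. If the true CL ratio were 1.20 at equal volume, the apparent ratio would be 1.278 at 24 days (1.278/1.20 = 1.065) and 1.328 at 10 days (1.328/1.20 = 1.107), a distortion of about 6% to 11%.

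**The case against.** The strongest objection is that the SAP leaves the multiple-dose derivation undefined rather than defining a wrong one: it never says that dose means one weekly dose or that AUC∞ starts at the last dose. That is true, and the percentages depend on this reading. The other single-dose readings also fail, however. SAP 7.2 puts time zero at Day 1 dosing. One dose over AUC from Day 1 is too low by 1 − 1/5 = 80% or 1 − 1/3 = 67%. Dose over AUCτ of the last interval errs the other way, because only 1 − exp(−7nk) of steady state is reached: 64% (five doses) and 45% (three) at 24 days, 91% and 77% at 10 days. CL would be overstated by 57% and 120%, or by 10% and 30%. Cumulative dose over AUC from Day 1 is sound under linear kinetics, but nothing in SAP 9.4 points to it.

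Linear kinetics is an approximation. The sponsor's model builds on a target-mediated one, and AUC0–168 per mg in Protocol Table 16 falls from 503/12.5 = 40.2 at 12.5 mg to 4414/150 = 29.4 at 150 mg and 32984/1200 = 27.5 at 1200 mg. From 150 mg upward the departure is small, and it does not change the direction.

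The discretion in SAP 9.2 to withhold parameters applies to concentration data that cannot be evaluated. These profiles can be evaluated; the formula is at fault. The protocol does leave detail to the SAP, so the missing entries in SAP 9.6 and 14 are the weaker part of the point. SAP 9.2 also names Day 29 derivation for Cohort 8 only, so the Cohort 9 comparison presumes a profile that it does not list.

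The limited stakes stand. The models in SAP 9.5 use Cmax and AUC, not CL or Vd, and the accumulation ratio would be reported alongside.

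**Conclusion.** The point holds. As written, the SAP extends CL/F and Vd/F to the multiple-dose cohorts with formulas valid only after a single dose, and its reliability screen passes the affected values. On the last-dose profile both parameters are about 58–71% too low after five weekly doses and 50–60% too low after three. This assumes one weekly dose as the numerator, linear kinetics and a half-life of 10 to 24 days, of which only the 24 is in the documents. Absorption, and the protocol's own predicted accumulation, make the error slightly larger.

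The harm is confined to these descriptive parameters and their comparison with single-dose values. It should be fixed, but it does not threaten the primary safety objective or any escalation decision, and the Cohort 9 versus 8 ratio is little affected.

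**What to change.** Do one of the following in SAP 9.2 and 9.4:

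1. Restrict CL/F and Vd/F to single dose, as in Protocol 9.4.3.1.
2. Define the multiple-dose CL/F as total dose given divided by AUC from the first dose to infinity, and Vd/F as that CL/F divided by λz. With n doses of size D, linear kinetics gives nD/(n·F·D/CL) = CL/F, so carry-over causes no bias. The intermediate weeks are sampled to 24 h and then at the next pre-dose, so state that the trapezoidal rule runs across them.

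Do not substitute dose/AUCτ, since steady state is not reached. AUC∞ after the last dose may stay as an exposure measure if it is labelled as including carry-over and is not compared with single-dose AUC∞. If the multiple-dose parameters are kept, record the extension beyond the protocol in SAP 9.6 and 14.

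The cost is an edit to SAP text and one table. No new data are needed, because PK samples already run from Day 1 to Day 155.

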9.4.1. PK Parameters Summarization

Pharmacokinetic parameters derived from serum concentrations will be presented in data listings and summarized separately by cohort/actual treatment using the following descriptive statistics: number of participants, arithmetic mean, STD, arithmetic CV, geometric mean, geometric CV, median, minimum, and maximum.

This document is confidential.

9.5. Planned Statistical Models for PK Parameters and Concentrations

The primary PK analysis will be based on the PK Set.

For the cohort 4 versus cohort 5 evaluation of the absolute bioavailability, the PK parameters (C_{max} , AUC_t , and AUC_{∞}) will be evaluated using an ANOVA statistical model with cohort, treatment, and sequence as the fixed effects, and participant-participant (sequence) as a random effect, using the natural logarithms of the data. Confidence intervals (CI, 90%) will be constructed for the least squares geometric mean ratio (GMR) for the cohort 4 versus cohort 5 for all 3 parameters using the natural log-transformed data. The GMRs and associated 90% confidence limits will be exponentiated back to the original scale.

The within-participant CV for the C_{max} , AUC_t , and AUC_{∞} will be estimated using the mean squared error from the ANOVA.

In addition, the geometric means and the associated 95% CIs of C_{max} , AUC_t , and AUC_{∞} will be reported for each treatment.

The evaluation of relative bioavailability, will be done for cohort 9 versus cohort 8 (for a comparison of non-Japanese versus Japanese descent).

All secondary analyses will be based on the PK Set.

Dose-proportionality will be assessed across all single dose (SD) cohorts (Cohort 1 (12.5 mg), Cohort 2 (50 mg), Cohort 3 (150 mg), Cohort 4 (450 mg), Cohort 6 (1200 mg) and Cohort 7 (\leq 2250 mg) ALXN1820) graphically and by using a power model (Smith, 2000; Newlands, 2006; EMA, 2010).

The following dose-normalized PK parameters will be assessed for dose proportionality: C_{max_n} , AUC_{t_n} and AUC_{∞_n} . The log (PK parameters) will be included as a response variable and log (dose) will be included as a fixed effect in the power model.

The form of the model is as follows:

PK Parameter = $e_{\alpha} \times \text{Dose}^{\beta} \times e_{\epsilon}$, where $\text{Dose} \geq 0$, and e_{ϵ} represents the associated error. Thus, perfect dose proportionality is met when $\beta=1$ (ignoring error). This becomes a linear relationship following a natural-log transformation, to which a linear regression will be fit by ordinary least squares (OLS):

$\ln(\text{PK Parameter}) = \alpha + \beta \times \ln(\text{Dose}) + \epsilon$, where $\text{Dose} > 0$, and ϵ represents the associated error.

The estimate of β together with a 90%CI will be provided (for each PK parameter model), and this will be used to quantify dose proportionality. According to Hummel et al. (2009), the following criterion may be used for exploratory dose proportionality evaluations: If the (two-sided) 90% CI for β is wholly contained within the interval, $[1+\ln(0.5)/\ln(\rho), 1+\ln(2)/\ln(\rho)]$, then dose proportionality is suggested across the investigated dose range. Here, ρ is defined as the ratio of the highest to lowest dose. This interval criterion will be reported along with the corresponding 90% CI estimate for β (presented to three decimal places).

$\log(\text{PK Parameter}) = \mu + \beta \times \log(\text{Dose})$

*where $\beta = 1$ indicates perfect dose proportionality. Estimation of β , along with its 90% CI, will be provided.

This document is confidential.

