^d Dosing in Cohort 5 is dependent on Investigator review of safety data through Day 8 (168 hours) of Cohort 4. However, should there be safety findings of concern in previous cohorts, an SRC review will be conducted for Cohort 5 to determine if participants will be dosed at the planned dose of 450 mg IV or a lower dose.

^e Dosing in Cohorts 8 and 9 to be determined based on SRC review of all data from the Day 15 (336 hours) assessment for Cohorts 4 and 5. Dosing of Cohort 9 may start at the same time as Cohort 8 or later depending on scheduling at the clinical site

^f Dosing in Cohort 10 to be determined based on SRC review of all data from the Day 29 (672 hours) assessment for Cohort 8 and PK/PD data from Day 29 (672 hours) after dosing of Cohorts 4 and 5.

Abbreviations: IV = intravenous; PD = pharmacodynamic; PK = pharmacokinetic; QW = once weekly; SC = subcutaneous; SP = syringe pump; SRC = safety review committee.

An SRC, consisting of the Investigator, Medical Monitor, safety physician, study statistician and clinical pharmacologist, will evaluate the available study data at prespecified time points for participant safety and make recommendations on dose escalation, dose modification, or

termination of the study (see SRC charter for description of membership, schedule of meetings, data required for each safety review, and requirements for documenting meeting discussions and outcome). At the Sponsor's discretion, and after consultation with the SRC, up to 18 additional participants across the entire study may be enrolled as replacement participants if a participant discontinues prior to Day 43 for reasons other than drug-related AEs.

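### SAP 9.5 fits a crossover ANOVA to two parallel single-dose cohorts, so its within-participant CV cannot be estimated; the interval level and dose basis for absolute bioavailability also need settling

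*SAP*

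**What the plan says.** Absolute bioavailability of the SC form is a secondary objective. Protocol 4.2 states its design basis: "The ALXN1820 IV cohort will provide the reference arm for assessing ALXN1820 SC absolute bioavailability".

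- **Model (SAP 9.5).** Cmax, AUCt and AUCinf for Cohort 4 versus Cohort 5 are to be "evaluated using an ANOVA statistical model with cohort, treatment, and sequence as the fixed effects, and participant-participant (sequence) as a random effect", on log-transformed data. The within-participant CV of the three parameters "will be estimated using the mean squared error from the ANOVA".
- **Interval (SAP 9.5).** "Confidence intervals (CI, 90%) will be constructed for the least squares geometric mean ratio (GMR) for the cohort 4 versus cohort 5", for all three parameters. The 95% intervals mentioned next in that section belong to each treatment's own geometric mean, not to the ratio.
- **Interval (SAP 9.2, with the same sentence in Protocol 9.4.3.1).** "For the absolute bioavailability estimates, a 95% CI for each of the ratio of the geometric means will be provided".
- **Definition of F (SAP 9.2 and Protocol 9.4.3.1).** "The absolute bioavailability for the ALXN1820 SC cohorts will be defined by the ratio of the geometric means" of AUC from zero to infinity, SC over IV. Neither text mentions dose normalization.
- **Design.** SAP 4.1 has 10 cohorts of 8 (6 active, 2 placebo), 80 in all. On timing, Protocol 4.1 says "Dosing in Cohort 5 is dependent on Investigator review of safety data through Day 8 (168 hours) of Cohort 4", and the same table footnote, with Protocol 4.3 and Table 19, allows Cohort 5 to be dosed at 450 mg IV or lower. On PK values, SAP 9.2 says "For the single dose cohorts 1-7, PK parameters will be derived on Day 1".
- **Declared changes.** SAP 9.6 and SAP 14 both record none.

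**The concern.** Sequence, participant within sequence and a within-participant CV belong to a crossover, in which each participant receives both treatments in a randomized order. Cohorts 4 and 5 are parallel groups, and neither document defines a sequence or period for them. A programmer following SAP 9.5 has to drop or improvise terms, and one required output does not exist in these data. If a number is printed for it anyway, a reader might use it as a within-participant CV, for example to size a later crossover study, when it is nothing of the kind.

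Two further points bear on the same result. The reported interval for F depends on which SAP section is followed. The ratio as defined equals F only when the SC and IV doses are equal, which the protocol does not guarantee.

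**Working it through.** **1. What the model can estimate**

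Inputs: 6 active participants in each cohort, one dose each, one value per parameter. The cohort arithmetic agrees with the stated totals: 10 × 8 = 80, 10 × 6 = 60 active, 10 × 2 = 20 placebo. Nobody is counted in two cohorts.

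Let x = 0 for Cohort 4 and x = 1 for Cohort 5.

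- Cohort is x. Treatment (SC or IV) is x. The only sequence a participant can have is the single treatment received, again x.
- The fixed part [1, x, x, x] has 4 columns and rank 2. Without participant terms, residual df = 12 − 2 = 10.
- If participants are coded as 12 indicators, the rank is 12 and residual df = 12 − 12 = 0.
- If participant is random, as the SAP says, each log value has variance σb² + σw² (between plus within). With one value per participant only the sum is identified.
- The contrast in x remains estimable. With one value per participant, the least squares ratio is simply the ratio of the two geometric means.

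**2. What would be printed as the within-participant CV**

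With 10 df the MSE estimates σb² + σw², so the printed figure is about √[(1 + CVb²)(1 + CVw²) − 1]. The documents give no CV, so these are assumed values. Example: √(1.09 × 1.01 − 1) = √0.1009 = 31.8%.

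| Assumed between CV | True within 5% | 10% | 20% |
|---|---|---|---|
| 20% | 21% | 22% | 29% |
| 30% | 30% | 32% | 37% |
| 40% | 40% | 41% | 45% |

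**3. 90% against 95% for the AUCinf ratio**

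The fold-width is exp(t × σ × √(1/n4 + 1/n5)), with σ² = ln(1 + CV²). On the log scale the ratio of widths is t(0.975)/t(0.95), whatever the CV:

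- 6+6 (10 df): 2.228/1.812 = 1.23
- 6+5 (9 df): 2.262/1.833 = 1.23
- 5+5 (8 df): 2.306/1.860 = 1.24
- 4+4 (6 df): 2.447/1.943 = 1.26

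The smaller cases matter because SAP 9.4 excludes unreliable AUCinf values from summary. For 6+6 and a ratio of 1.00:

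| Assumed CV | 90% CI | 95% CI |
|---|---|---|
| 20% | 0.813–1.230 | 0.775–1.290 |
| 30% | 0.736–1.360 | 0.685–1.459 |
| 40% | 0.668–1.497 | 0.609–1.641 |

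**4. Dose basis of F**

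If AUCinf is proportional to dose, the un-normalized ratio is F × (SC dose / IV dose). At 450 mg for both, it equals F. If Cohort 5 receives a lower IV dose D, the ratio becomes F × 450/D, which exceeds F.

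Proportionality is an assumption. The documents give no AUCinf, and the predicted AUC over 0–168 h in Protocol Table 16 is not proportional at low doses: 503/12579 = 0.040 at 12.5 mg against 12.5/450 = 0.028 by dose, and 1685/12579 = 0.134 at 50 mg against 50/450 = 0.111.

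**The case against.** - **The ratio survives.** The ratio of geometric means can be estimated once the aliased terms are dropped. A reader might infer that the bioavailability objective cannot be met, or that the analysis has no residual df. The documents support neither. Zero df arises only if participants are coded as fixed indicators, and the SAP makes them random. What the software prints depends on settings that neither document states. The mislabelled CV remains in every case.
- **Both intervals can be produced.** SAP 9.2 keeps the protocol's 95% interval, SAP 9.5 does not withdraw it, and Protocol 9.4.3.1 leaves further detail to the SAP. A reader might infer that the protocol's 95% interval was replaced without declaration. On the plain reading nothing was dropped, and the entries of no change in SAP 9.6 and 14 can stand on this point. What remains is that two levels apply to one ratio and the SAP does not say which is reported for F. The 90% intervals for Cmax and AUCt conflict with nothing.
- **F at other doses is probably not planned.** The plural reference to SC cohorts in SAP 9.2 might suggest an un-normalized F at every SC dose. That is only one reading: the definition ends in the singular, SAP 9.5 models Cohort 4 versus Cohort 5 only, and Protocol 4.3 ties the IV dose to the 450 mg SC cohort. The possibility of a lower IV dose is in the protocol itself, so the dose-basis point stands for the intended pair.

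**Conclusion.** The model specification is wrong as written. The fixed terms are aliased (rank 2 of 4), the within-participant CV is not estimable, and the MSE is total, mainly between-participant, variance. This follows from the design and needs no assumed values. The CVs in the working only illustrate the size of the mislabelling, such as about 32% printed where the true within-participant CV is 10% and the between-participant CV is 30%.

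The interval level for the AUCinf ratio is unreconciled, and the choice changes the log-scale width by a factor of about 1.23 at 10 df. The definition of F holds only for equal doses; whether that matters for Cohort 4 versus Cohort 5 depends on the IV dose actually given.

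This is an error of specification and labelling in a named secondary objective. Protocol 9.1 states no hypotheses, no decision rule uses F, and the objective can still be met.

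**What to change.** 1. In SAP 9.5, fit ln(parameter) with cohort (which is route) as the only factor, in the active participants of Cohorts 4 and 5. This gives 10 df if 6+6 are evaluable.
2. Delete treatment, sequence, the participant random effect and the within-participant CV sentence, or relabel that CV as between-participant. SAP 9.4.1 already provides a geometric CV by cohort.
3. Name the 95% interval as the one reported for the AUCinf bioavailability ratio. The 90% interval may be shown in addition, and may stay for Cmax and AUCt.
4. Compute F from dose-normalized AUCinf, which the SAP already defines, with Cohort 4 versus Cohort 5 as the stated comparison. At equal doses the normalization cancels and changes nothing. At unequal doses it relies on dose proportionality, so that assumption should be stated beside the estimate.
5. If F is not reported for the other SC cohorts, record that in SAP 9.6 and 14.
6. Minor: SAP 9.5 describes Cohort 9 versus Cohort 8 as non-Japanese versus Japanese. Cohort 9 is the Japanese cohort, so the label should be reversed.

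The cost is SAP wording and simpler code, with no new data. The reported AUCinf interval is about 23% wider on the log scale than the 90% interval.
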